4.4 Withdrawal and discontinuation

Participant are withdrawn from the study if:

- Parent withdraws informed consent.
- Other legal representative (parent) is in disagreement with participation.
- Major protocol deviation occurs in disrespect of inclusion criteria.

Co-investigators are to inform principle and chief investigator of protocol deviation within 24h after they are acknowledged. Withdrawal are to be noted in patient records. Contact details can be kept by co-investigators that follow patients but are to be removed from all other documents (principle and chief investigator list).

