5 STATISTICS AND METHODOLOGY

5.1 Statistical analysis plan and sample size calculation

The analysis of the data will be carried out on the entire data collected by the international consortium. The Swiss data is therefore embedded in the overall analysis.

Sample size estimation

The data collected on crying time and standard deviations (SD) during the pilot phase (n=13, one diary was completed incorrectly) was consistent with observations made by (Wolke et al., 2017). We estimated the average daily crying time over the two-week follow-up period to be 120 minutes with a SD of 46 minutes. To detect a minimum of 30 minutes additional reduction in crying time between the intervention and control groups, with 90% power and a two-sided 5% significance

level, we would need 48 infants in each arm of the trial. If we allow for a 15% drop-out rate, we would need to randomise 112 infants or 56 in each arm. Each country is expected to enrol 40 participants or four patients from 10 secondary sites.

Descriptive statistics

Descriptive statistics will be used to summarise the characteristics of participants in each group in the trial. This will include baseline values, treatment schedules, compliance and follow-up. We will show number and percentage or mean and standard deviation for categorical and normally distributed continuous variables respectively. For data severely deviating from a normal distribution, we will present median and interquartile ranges. Probability of observed between groups difference will be calculated by using Fisher's exact, Chi2 test, Mann Whitney U test and, or Student's t-test as appropriate.

For crying time, the Bartlett's periodogram-based test for white noise will be used to test the assumption of constant mean and variance for each individual. Analysis of graphical representation will define which transformation would best model trend over time. If a clear change of effects happens abruptly over time, the data will be additionally analysed over separate time periods, by default separating the first week from the second. If such a trend exists, secondary analysis will also compare differences for indicators of this trend between groups.

Primary outcome analysis

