Attrition bias could occur if the number of consultations is unevenly distributed between groups. Therefore, secondary analysis will verify that results are not influenced by uneven distribution of number of consultations. This will be done using random-effects generalised least-square regression adjusting for lack of independence at practitioner level.

Complementary confirmatory analysis

- Separate analysis between 1st and 2nd week (stratified analysis underpowered).
- If baseline imbalance (p -value <0.10) is observed, a secondary analysis with adjustment for these variables will be run to confirm results.
- Per protocol analyses.

All analysis will be intention-to-treat (ITT) except for a secondary per protocol analysis on the primary outcome. All P values will be two sided, and the significance level set at 5%. All statistical analysis are to be done using StataCorp. 2017. Stata Statistical Software: Release 15. College Station, TX: StataCorp LLC. Statistical analysis is managed by [name] who is responsible of preprogramming the entire analysis prior to data collection, of justifying protocol deviation and obtaining approbation from the trial steering committee whilst still blinded from allocation, of running the analysis and delivering the statistical report.

Stopping rule

There are no statistical stopping rule. The trial will be stopped if another high-quality definitive research trial shows that this type of intervention is either highly effective, or is harmful and renders the continuation of this trial inappropriate. The Data Monitoring Committee (DMC) will review the data after 75 infants have been recruited and followed up, to determine progress. The trial will not proceed if more than half the parent participants do not complete their crying diaries, withdraw from the study or if the DMC considers that participants experience too many serious adverse events.

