5.2 Handling of missing data and drop-outs

Missing data from diaries will be accepted if at least eight separate entries over two weeks are provided. The average daily crying time will then be provided by averaging the crying time over the available days. As missing data cannot be assumed to be missing at random, complete case analysis is to be done. A sensitivity analysis will then evaluate effects on results with the worst-case scenario (imputation of highest observed effect if in control and lowest if in OMT group).

Drop-outs from treatment are to be followed-up and questionnaires delivered as if treatment had continued (ITT approach). Data from participants who have dropped-out or could not be followed will be replaced by new subjects.

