8.3 Confidentiality and coding

Trial and participant data will be handled with uttermost discretion and is only accessible to authorised personnel who require the data to fulfil their duties within the scope of the study. On the CRFs and other study specific documents, participants are only identified by a unique participant number.

CastorECD automatically attributes a code to each participant. They are generated sequentially and automatically by Castor EDC for each site (Switzerland is a single site). The format is XXXNNNNN where XXX is an institution code and NNNNN is the number part. There is no way to know what time and day it was generated purely from the code.

The data collected up to the withdrawal of the study will be used, so as not to compromise the value of the study as a whole.

Participation identification lists are stored by co-investigators. These lists also include contact details such as telephone numbers and E-mail addresses. Each co-investigator is responsible of keeping a secured paper form list of participants they have recruited. Upon completion of the trial, for future legal purposes, the participant list linking IDs to patients are archived by co-investigators. Consent forms are to be kept for at least 25 years with the patient record.

Practitioners do not have access to participant questionnaires. Chief and principal investigators have access to the coded electronic data. Once cleaned by the UCO data clerk, anonymised data is to be made available to the statistician.

Data made available to co-authors or reviewers are coded and not given in sufficient detail to be able to identify participants.

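### The rule that drop-outs and infants lost to follow-up are replaced by new subjects contradicts the planned intention-to-treat analysis and duplicates the 15% drop-out allowance

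*Protocol*

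**What the plan says.** The replacement rule closes section 5.2 of the protocol: "Data from participants who have dropped-out or could not be followed will be replaced by new subjects".

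Five other statements bear on the same infants:

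- **Section 5.1, analysis population:** "All analysis will be intention-to-treat (ITT) except for a secondary per protocol analysis on the primary outcome".
- **Section 5.2, the sentence directly before the rule:** "Drop-outs from treatment are to be followed-up and questionnaires delivered as if treatment had continued (ITT approach").
- **Sections 5.1 (Sensitivity analyses) and 5.2:** a worst-case analysis imputes unfavourable crying times for infants lost to follow-up or without a primary outcome. Section 5.1 describes it as ITT.
- **Section 8.3:** "The data collected up to the withdrawal of the study will be used".
- **Section 5.1, sample size:** "If we allow for a 15% drop-out rate, we would need to randomise 112 infants or 56 in each arm".

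Two further rules decide who reaches the primary analysis. Section 5.2 sets a diary threshold, "Missing data from diaries will be accepted if at least eight separate entries over two weeks are provided", and then says "As missing data cannot be assumed to be missing at random, complete case analysis is to be done". Section 4.4 lists, among the grounds for withdrawal, "Major protocol deviation occurs in disrespect of inclusion criteria".

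**The concern.** An intention-to-treat comparison keeps each randomised infant in the arm to which it was allocated. A rule that substitutes another infant's data because of something that happened after allocation works against this. The protocol also makes the statistician responsible for programming the whole analysis before data collection, and that cannot be done consistently while section 5.2 both follows treatment drop-outs and replaces them.

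Two things are at stake. The first is who is in the primary comparison, above all an infant who stopped treatment but whose parent completed the diary. The second is whether attrition stays visible. If losses are topped up with new infants, the analysed numbers look complete while the selection behind them is unchanged. Section 5.2 itself does not accept that data are missing at random.

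**Working it through.** **1. The statements side by side**

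| Infant | Other statements | Replacement sentence |
|---|---|---|
| Stops treatment, diary has at least 8 days | Followed up and analysed as randomised (5.1, 5.2) | Data replaced, if dropping out includes stopping treatment |
| Withdrawn, some diary data | Data to that point used (8.3) | Data replaced |
| Lost, too few diary days | Not in the complete-case analysis, imputed in the worst-case analysis (5.1, 5.2) | Data replaced, so nobody is left to impute |

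Taken literally, the sentence conflicts with another statement in every row.

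**2. The plan's own sample size**

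Inputs from section 5.1: difference 30 min, SD 46 min, two-sided 5%, power 90%, drop-out 15%. Enrolment of 120 in a 1:1 ratio is from section 4.1.

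- n per arm = 2 × [46 × (1.960 + 1.282) / 30]² = 49.4, rounded up to 50. The protocol states 48, which is close. Power at 48 per arm is 89.2%.
- Inflation: 48 × 1.15 = 55.2, giving 56 per arm and 112 in total, as stated. Dividing instead gives 48 / 0.85 = 56.5, so 57 per arm and 114 in total. The difference is immaterial here.

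**3. Is replacement needed for power?**

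- 120 randomised is 60 per arm, and 60 × 0.85 = 51 per arm after the planned loss.
- Standard error = 46 × √(2/51) = 9.11 min. Power = Φ(30/9.11 − 1.96) = Φ(1.33) = 90.9%.
- With 112 randomised, 56 × 0.85 = 47.6 per arm, in line with the planned 48.

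These figures ignore clustering by practitioner and site, as the protocol's own calculation does. The allowance already covers the planned loss of 0.15 × 112 = 16.8 or 0.15 × 120 = 18 infants. Replacing until 112 or 120 infants complete would instead mean randomising 112 / 0.85 = 131.8 (132) or 120 / 0.85 = 141.2 (142).

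**4. Does replacement reduce attrition bias?**

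Let d be the fraction lost in an arm and Δ the excess crying of lost infants over completers. The completer mean lies below the full-arm mean by d × Δ, so the between-arm difference is biased by the difference in d × Δ between the arms. The number of substitutes does not enter. New infants pass through the same follow-up, and those analysed are again completers.

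Illustrations, with inputs that are assumed and not in the protocol:

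- Loss differs by 10 points between arms and Δ is 23 to 46 min (0.5 to 1.0 SD) in both: 0.10 × 23 = 2.3 min to 0.10 × 46 = 4.6 min, or 8% to 15% of the 30 min target.
- Loss is 15% in both arms and Δ differs between arms by 15, 30 or 46 min: 0.15 × 15 = 2.3, 0.15 × 30 = 4.5 and 0.15 × 46 = 6.9 min. With 48 completers per arm (standard error 9.39 min), the two-sided type I error is then about 5.7%, 7.7% or 11.4%.
- Equal loss and equal Δ in both arms: zero.

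These amounts arise under the complete-case rule with or without replacement.

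**The case against.** The best defence is that the sentence is clumsy wording for topping up recruitment. Treatment drop-outs are expressly followed up, and the worst-case analysis presupposes that lost infants stay in the data set. Dropping out could also mean leaving the study and not merely stopping treatment. This reading is possible, but the text speaks of replacing the data of those participants and does not describe additional recruitment. The wording still has to be reconciled.

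A second objection stands in full. The restriction to completers comes mainly from the eight-entry threshold and the complete-case rule. Without the replacement sentence, an infant with too few diary days would still be missing from the primary analysis.

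A reader might be tempted to go further in four ways that the protocol does not support:

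- **That replacement causes a bias of 2.3 to 4.6 min.** That figure is attrition bias under assumed inputs, and replacement neither creates nor removes it.
- **That section 4.4 removes ineligible infants from the analysis after randomisation.** It does not say after randomisation. Late discovery is likely, since health and consent are confirmed before allocation (section 4.3), but this is inference. Section 8.3 keeps data up to withdrawal, so a withdrawn infant with eight diary days could still be analysed.
- **That unblinded osteopaths decide on such withdrawals.** Section 4.4 has them report deviations to the principal and chief investigators, who are blinded according to section 4.3. It names no decision-maker.
- **That a substitute would be forced into the vacated arm and so reveal the allocation.** No forced allocation is described. Blocks of 4 and 6 are generated in real time by the platform.

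**Conclusion.** The replacement sentence is wrong as written. It contradicts the ITT declaration in section 5.1, the sentence before it in section 5.2, the worst-case analysis and section 8.3. It also provides again for a loss that the 15% inflation already covers. Its direct effect on the primary comparison is confined to infants whose usable data would be set aside, notably those who stop treatment but keep a diary. The protocol does not split the 15% between stopping treatment and losing the diary, so the number of such infants cannot be given. For the remainder, replacement hides attrition without correcting it.

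The firm figure is that replacement is not needed for power: 51 per arm after 15% loss from 120, about 91% on the protocol's unclustered assumptions. The bias figures only illustrate what unequal attrition could do under the complete-case rule. Section 4.4 is not shown to exclude anyone from analysis, but it leaves the analysis status of infants later found ineligible unstated, and one line would settle that.

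**What to change.** Delete the replacement sentence from section 5.2 and state in its place that:

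- every randomised infant stays in the allocated arm and in the ITT set;
- available diary data are used, as section 8.3 says;
- infants lost to follow-up enter the worst-case analysis;
- the drop-out allowance in section 5.1 covers losses, and any further infants are additional randomised participants, reported as such, and substitute for nobody.

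Beside the eligibility ground in section 4.4, add only that infants later found not to meet the inclusion criteria stay in the ITT analysis with the data available and are excluded from the per-protocol set alone. The withdrawal grounds for consent and for disagreement of the other legal representative stay unchanged. No rule on treatment is needed.

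These changes do not cure the completer restriction, so the report should call the primary analysis complete-case and show losses by arm. The cost is a wording amendment with no extra infants beyond the planned 120. The downside is that a few ineligible infants remain in the ITT set, with slight dilution of the effect.

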6 REGULATORY ASPECTS AND SAFETY

6.1 Local regulations / Declaration of Helsinki

This study is conducted in compliance with the protocol, the current version of the Declaration of Helsinki, the ICH-GCP, the HRA as well as other locally relevant legal and regulatory requirements.

6.2 (Serious) Adverse Events

An Adverse Event (AE) is any untoward medical occurrence in a patient or a clinical investigation subject which does not necessarily have a causal relationship with the trial procedure. An AE can therefore be any unfavourable or unintended finding, symptom, or disease temporally associated with a trial procedure, whether or not related to it.

A Serious Adverse Event (SAE) (ClinO, Art. 63) is any untoward medical occurrence that

- Results in death or is life-threatening,
- Requires in-patient hospitalisation or prolongation of existing hospitalisation,
- Results in persistent or significant disability or incapacity, or
- Causes a congenital anomaly or birth defect

Both Investigator and Sponsor-Investigator make a causality assessment of the event to the trial intervention, (see table below based on the terms given in ICH E2A guidelines). Any event assessed as possibly, probably or definitely related is classified as related to the trial intervention.

Relationship	Description
Definitely	Temporal relationship Improvement after dechallenge* Recurrence after rechallenge
Probably	Temporal relationship Improvement after dechallenge No other cause evident
Possibly	Temporal relationship Other cause possible
Unlikely	Any assessable reaction that does not fulfil the above conditions
Not related	Causal relationship can be ruled out
*Improvement after dechallenge only taken into consideration, if applicable to reaction	

Both Investigator and Sponsor-Investigator make a severity assessment of the event as mild, moderate or severe. Mild means the complication is tolerable, moderate means it interferes with daily activities and severe means it renders daily activities impossible. Adverse events are to be classified using an agreed taxonomy for manual therapy drawn from a consensus study (Carnes et al. 2010).

Reporting of SAEs (see ClinO, Art. 63)

All SAEs are documented and reported immediately (within a maximum of 24 hours) to the Chief-Investigator of the study (international investigator) by the Principle-Investigator (site investigator Switzerland).

Adverse event monitoring will be done by the treating osteopaths, scrutiny of the follow up questionnaires and contact with the study principal investigator (PI) who may receive complaints or concerns from parents/carers directly. An independent reporting mechanism to a person independent of the trial's study team also exists (details are provided on the participant information sheet). An adverse event report will be generated within 24 hours for any unwanted or unexpected incident, event or accident that is reported. In the case of serious adverse events such as death or unplanned hospital admission, an adverse event report will be generated immediately for both the local and the international sponsors.

In Switzerland, the Swiss Principal Investigator is responsible for reporting events to the local sponsor, the Chief investigator and the local Ethical Committee. If it cannot be excluded that the SAE occurring in Switzerland is attributable to the intervention under investigation, the local Principal Investigator reports it to the Ethics Committee via BASEC within 15 days. Decisions regarding stopping the trial on all sites are to be made by the main sponsor following the UK ethical standards with the NHS (DMC and NHS ethical board).

Follow up of (Serious) Adverse Events

Principal investigators at a national level are to monitor evolution of conditions for participants terminating the study with SAEs. This is done in close collaboration with co-investigators. Patients or parents are contacted by phone or E-mail, depending their preferences, until resolution or stabilisation. This is to be done once a month for the first six months and once every three months afterwards.

Even in the absence of adverse events, After the 14 day period of the trial. The parent can make decisions about their child's onward osteopathic care should they deem it appropriate, this care would be delivered and priced as per normal clinic practice. All other care will continue as normal during the trial and after.

6.3 Safety reporting

For the Swiss part of the study, an annual safety report (ASR/DSUR) will be submitted once a year to the local Ethics Committee by the Investigator (ClinO, Art. 43 Abs). Given the study is not to last more than a year, a single report is planned for December 2021. This report will include information on SAE from all sites including those out of Switzerland.

The Swiss site is a secondary site. All SAE from the three national sites are reported to the Chief Investigator using ICH E2A standards as required by the NHS. SAE from other countries are therefore not reported using the ASR/DSUR.

6.4 Amendments

Substantial changes to the study setup and study organization, the protocol and relevant study documents are submitted to the Central Ethics Committee for approval before implementation. Substantial amendments are changes that affect the safety, health, rights and obligations of participants, changes in the protocol that affect study objective(s) or central research topic, changes of study site(s) or of study leader and sponsor (ClinO, Art. 29). A list of substantial changes is also available on www.swissethics.ch.

The Central Ethical Committee capable of approving changes is the London – Survey Research Ethics Committee linked to the NHS Health Research Authority. Local ethical Committees are to be informed of the approved changes.

Under emergency circumstances, deviations from the protocol to protect the rights, safety and well-being of human subjects may proceed without prior approval of the Ethics Committee. Such deviations shall be documented and reported to the local and central Ethics Committee as soon as possible.

A list of all non-substantial amendments will be submitted in December 2021 to the competent EC together with the ASR.

6.7 (Premature) termination of study

The Sponsor-Investigator may terminate the study prematurely according to certain circumstances, e.g.

- Ethical concerns,
- Insufficient participant recruitment,
- When the safety of the participants is doubtful or at risk (e.g. when the benefit-risk assessment is no longer positive),
- Alterations in accepted clinical practice that make the continuation of the study unwise, or
- Early evidence of harm or benefit of the experimental intervention

Upon regular study termination, the Ethics Committee is notified via BASEC within 90 days (ClinO, Art. 38). Upon premature study termination or study interruption, the Ethics Committee is notified via BASEC within 15 days (ClinO, Art. 38).

7 FURTHER ASPECTS

7.1 Overall ethical considerations

Ethical approval

- For the pilot phase, ethical appraisal and approval was granted by University College Osteopathy Ethics Committee (05.06.19) Ref: CUTIES trial.
- The main trial received ethical approval from the London-Surrey National Health Service Research Ethics Committee: IRAS # 268925 19/LO/1620 (09.11.19). This organisation is the Central Ethical Committee for the trial.
- The Australian arm of the trial received ethics approval from Southern Cross University Human Research Ethics Committee (HREC), approval number 2019/569.
- The Swiss arm of the trial received ethical approval from Swiss Ethics, approval number 2021-00099

Public and participant involvement

Parents of infants who are 'colicky' or who have been labelled with 'silent reflux' were consulted about the design of the study, particularly the interventions and blinding. All the participant facing material has undergone review by two women who have recently experienced birth and cared for a distressed infant. They reviewed the material and made some insightful comments and suggestions to improve the participant information leaflet, the recruitment poster and the trial questionnaires. A patient representative also sits on the trial management committee and the trial steering committee. Where possible, parents will be involved in the dissemination of the results of the trial by contributing to presentations.

Self-limiting condition in healthy infants

Some people may argue that as 'colic' is a self-limiting condition in most cases there is no point in treating these infants or indeed researching the topic. The reality is however that there are practitioners 'treating' infants with colic and there is a demand from parents for 'treatment' and or additional support. These practitioners in private practice will also charge for the care. Parents need robust information and evidence to be able to make informed decisions about the care of their infants.

Consent of infants

Parent participants will not be enrolled in the trial unless consent is informed and valid. All participants will be given a participant information leaflet and access to the study team and their osteopath should they have questions about their involvement. The infant will have a specific trial case record form to which the study team will seek consent to access, no request for access to other personal medical records of the infant or the parent will be sought.

Child protection

In terms of child protection, participating osteopaths will need to be registered osteopaths and therefore be considered to be able to treat children. The risks to the infants from the manual therapy treatment are low (Carnes et al., 2018; Carnes, Mars, et al., 2010), however the study team are aware that parents can have strong emotional reactions. We will therefore ensure that our training course for osteopaths includes distress management. Should any parent participant become unduly distressed they will be helped by the osteopath who will listen and support the parent until they are sufficiently able to leave the consultation room and care for their infant. However, we recognise that in some circumstances it may be necessary, and with the participant's agreement, to seek further help from a more suitable health care professional. Under no circumstances will an infant or parent be left unduly distressed. If the osteopath feels that the parent participant is a danger to themselves or others, they will seek permission to contact the parent participant's normal GP or take them to Emergency care. In terms of safeguarding each participating osteopath will be required to inform themselves of the 24/7 safeguarding procedures and contact numbers in their locality should they deem a child is at risk or if the parent is at risk of harming them-self or their child or children.

Safety

All interventions administered with therapeutic intent have some component potential to harm as the intent is to change something. This process of change can be considered from a biopsychosocial perspective. From a biological or physiological perspective the intervention and health screening is minimally invasive and gentle thereby reducing the risk of injury and creating an opportunity to identify any other conditions requiring referral to another health care professional. We are recruiting osteopaths who are experienced in treating infants and therefore we expect that they have made suitable modifications and arrangements in their clinical setting to accommodate treating infants. The minimum level of health and safety requirements will be addressed in the participating osteopath training courses, for example safeguarding, hygiene and cleanliness, use of toys to BSI UK and or EU standards and appropriate handling infants.

Psychological distress

Psychological distress is more probable at the parent level. Osteopaths participating in the study will be trained to observe the level of anxiety, stress and vulnerability of the parent and give appropriate best practice advice and action. In some unlikely cases, parent participants may be at risk of harming themselves or their infant. In this situation, in the first instance the osteopath will suggest the parent to seek further support for themselves (GP or appropriate family support or support group). At the next level should the parent be unsure about seeking help, the osteopath will offer, with the parent's permission to seek help on their behalf (GP or appropriate family support or support group). Should the patient refuse both these pathways and the osteopath is so concerned about the immediate safety of the parent or the infant, in Switzerland, they are to call the Cantonal Physician and explain the citation and ask whether they are authorised or not to break confidentiality and inform the family GP and or emergency social services.

Potential for coercion and or inducement

Free treatment may persuade some parents to seek osteopathic care where in other circumstances they may not consider it. Conversely it may increase equity (access) and therefore promote equality in care provision, as the traditionally white and middle class osteopathic clientele could be expanded to include other groups (C. A. Fawkes et al., 2014; Vaucher et al., 2018). All parent participants will be given written information supported by verbal information where requested and the study teams will be available to answer any questions potential participants might have. A 24 hour cooling off period will be given between the participant invitation and the final consenting process to be in the trial. Consent will be gained and counter signed via the treating osteopath, the consenting procedure will be addressed in the osteopath training course and in the Protocol for Osteopaths. Specific wording is given to reduce the potential for coercion giving the parent complete freedom to decide without quality of care being affected. If the parent feels induced by the free treatment we will ask the osteopaths to point out that they parent will be required to complete 2 questionnaire and complete a 14 day crying diary.

Information protection

Only the clinic staff and research staff (subject to the appropriate consent) will be able to view the infant's trial records. Initial contact will mostly be via osteopaths and, or an experienced member of the study team. Parents will have the choice whether or not to participate. All data will be collected using CastorEDC, a GDPR compliant solution designed for clinical trials by Ciwit B.V. and hosted in the Netherlands (ISO/IEC 27001 – 0025833).

